## 12.2 Secondary Objectives

- 12.2.1 To determine the test-retest reproducibility of quantitative assessment of tumor FFNP uptake.

The reproducibility of the two measurements of FFNP uptake will be evaluated in the 5 subjects who elect to undergo a second imaging session, using summary statistics of tumor FFNP uptake for each reading for PET/MRI. The analysis will be done separately for each reader.

- 12.2.2 To determine the intra- and inter-observer variability of quantitative assessment of FFNP.

The intra- and inter-reader agreement of SUV values for tumor FFNP uptake will be analyzed with Bland-Altman plots and 95% limits of agreement. Analyses will be conducted on a per-lesion basis, and repeat tumors within the same patient will be assumed to be independent.

- 12.2.3 To evaluate the optimal cut-point of FFNP uptake for distinguishing between PR negative and PR positive invasive breast cancer.

Receiver operating characteristic (ROC) curve analysis will be performed to determine the optimal cut-point for FFNP uptake to distinguish PR-positive from PR-negative invasive breast cancer, as

defined by the clinical pathology report. The area under the curve for the ROCs and their respective two-sided 95% confidence intervals will be calculated using logistic regression. The optimal cut-off point will be determined by considering the FFNP uptake value with the maximum sensitivity and specificity. The analysis will be done separately for each reader.

- 12.2.4 To estimate the association of tumor FFNP uptake (continuous SUVmax) with research-based Oncotype DX scores (0-100).

Scatter plots of continuous FFNP uptake (SUVmax) on the y-axis and research-based Oncotype DX scores (unitless) on the x-axis will be created to explore the distribution of the measurements. Pearson's or Spearman's rank correlation will be used to evaluate the association between FFNP uptake and research-based Oncotype DX score. The correlation coefficient (rho) and 95% confidence interval will be reported.

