## NUMBER OF SUBJECTS

---

[figure not shown]
\* Patients with newly diagnosed invasive breast cancer from a screening breast MRI are eligible to participate in this research. For these subjects, the research breast PET/MRI should be performed prior to any treatment or surgery for the invasive breast cancer.

The primary objective is to compare FFNP  $SUV_{max}$  from PET/MRI with the PR immunohistochemistry semi-quantitative score obtained by using the Allred score (0-8) (1). The correlation of the two measures will be evaluated with Pearson's correlation coefficient. The null hypothesis is  $H_0: p_0=0.20$  and the alternative hypothesis is  $H_1: p_1=0.70$ .

A sample size of 21 patients achieves 80% power to detect this difference, using a one-sided hypothesis test with a Type I error of 5%, accounting for 1 dropout. Up to 5 subjects with PR-negative breast cancer will be enrolled.

To measure test-retest reproducibility, a subset of up to 5 PR+ participants will have test-retest FFNP scans.

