A drawback of PET for imaging primary breast cancer is its limited spatial resolution. Magnetic resonance imaging (MRI), however, produces exquisitely detailed images of the breast due to its high spatial resolution. MRI evaluation of breast cancer is dependent on anatomic detail to characterize tumor morphologic characteristics and functional assessment of lesion perfusion, characterized by the time-dependent uptake and lesion enhancement with gadolinium contrast (dynamic contrast enhanced MRI). These features make breast MRI the most sensitive method for the detection of breast cancer (13). In contrast, CT does not offer the soft tissue differentiation necessary for evaluation of the breast. Thus, MRI has become the standard of care when an additional modality is necessary to evaluate for breast cancer. CT is not used in clinical practice to evaluate the breasts.

Combining PET with MRI leverages the benefits of both modalities for the evaluation of breast cancer. Simultaneously acquired MRI images assist with PET radiotracer dose reduction, which is a necessary, critical advancement for the translation of PET/MRI imaging of the breast to clinical practice. Our research team has developed and validated the imaging acquisition protocol and workflow for breast PET/MRI (14). The protocol accounts for MR attenuation correction, quantitative standardized uptake value (SUV) calculation using PET, motion correction, co-registration of the two imaging modalities, radiopharmaceutical dose reduction, and patient workflow considerations. Although this protocol was validated using F-fluorodeoxyglucose (FDG), it will be applicable for any novel molecular radiotracer to be imaged in combination with MRI, including FFNP.

It is important to validate the accuracy and reproducibility of quantitative tumor FFNP uptake measured using PET/MRI breast imaging. Further studies will be performed to test whether FFNP-PET/MRI can be used to distinguish patients with endocrine-sensitive from endocrine-resistant ER+ primary breast cancer. To the best of our knowledge, this study will be the first to investigate simultaneous breast PET/MRI imaging with FFNP for measuring PR expression in primary breast cancer.

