**Table 2: Study Calendar/Schedule**

Study Activity	Baseline a	Imaging Day b	Clinical Follow-Up c
Informed Consent h	X		
Demographics d	X		
Medical History d	X		X
Radiology Reports d	X		X
Pathology Reports (Breast biopsy and final surgical excision) d	X		X
Concomitant Medication Review		X	
Pre-Scan Pregnancy Test (if needed)		X	
Day of last menstrual period (if premenopausal)		X	
Height and Weight		X	
Vital Signs e		X	
Blood for Hormone Levels		X	
FFNP-PET/MRI i		X j	
Adverse Event Evaluation f		X	X
Research-based Oncotype DX Score g			X

- (a) Baseline is defined as the time period from initial subject contact until injection of FFNP.
- (b) Imaging Day is defined as the day of the research FFNP-PET/MRI session.
- (c) Any standard of care clinical visits, labs, or imaging exams obtained during this time period will be reviewed from the electronic medical record to correlate with scan results.
- (d) Clinical data, including age, primary breast cancer data (standard clinical histopathology including ER/PR/HER2/Ki-67, location, size, and date of biopsy/diagnosis), Oncotype Dx recurrence score (if obtained clinically), mammographic breast density, and menopausal status will be recorded. If premenopausal, menstrual cycle data will be recorded.
- (e) Vitals signs (blood pressure, heart and respiratory rate, and temperature) will be measured before FFNP injection, after FFNP injection, and after the PET/MRI scan.

- (f) Adverse events occurring within a 24-hour period post-FFNP infusion will be recorded by the study coordinator who will contact the subject within 1 to 3 days.
- (g) A research-based Oncotype DX assay will be performed using the resection specimen, if remaining tissue is available.
- (h) During the COVID-19 pandemic, consent procedures will be conducted by phone, when possible, to minimize face-to-face contact subjects have with the research team. An encrypted copy of the consent form will be mailed or emailed to subjects prior to the scheduled consent phone call.
- (i) Subjects who are unable to undergo a PET/MRI scan will be invited to undergo a PET/CT scan in addition to separate MRI scan.
- (j) For subjects participating in the test-retest cohort, the second scanning session will be done 24 hours apart or within a maximum 14-day time frame.

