### 5.5.6 Research Imaging Analysis

Two independent readers blinded to the clinical outcome will undergo two sessions of image interpretation of FFNP-PET/MRI scans separated in time by a washout period of at least 4 weeks. Images will be reviewed for general quality. The known biopsy-proven breast cancer(s) will be identified on the PET/MRI examinations based on its known location from the prior clinical breast MRI, if performed, or the patient's previous imaging, as is typically done in routine clinical practice. MRI will be used to localize the lesion(s), measure the lesion size (in three dimensions), and assign the region of interest (ROI) for PET imaging analysis. Each lesion will be analyzed for (1) qualitative appearance (visible above background or not) and (2) semi-quantitative FFNP uptake.

**Qualitative Analysis of FFNP uptake (lesion-level):** FFNP uptake will be evaluated qualitatively with the following grading scale: no uptake (tumor < background), minimal uptake (tumor = background), mild (tumor slightly > background), moderate uptake (tumor >> background), and intense uptake (tumor >>> background). Tumor uptake will also be dichotomized as increased (moderate or intense uptake) or absent (no uptake, minimal or mild uptake).

**Quantitative Analysis of FFNP uptake (lesion-level):** Standardized uptake values (SUV) will be measured by manually drawing a region of interest (ROI) to encompass the entire lesion guided by the lesion extent visualized on anatomic imaging. SUV analyses will include, but not be limited to,  $SUV_{\max}$  (maximum value),  $SUV_{\text{peak}}$  (small fixed-size ROI centered on most intense part of tumor),  $SUV_{\text{mean}}$  (average value), and  $SUV_{\text{sd}}$  (standard deviation). Tumor-to-normal tissue uptake ratios will also be measured. Other PET imaging parameters will include FTV (functional tumor volume; i.e. the volume of tumor tissue with increased FFNP uptake) and TLU (total lesion uptake; i.e. the product of  $FTV \times SUV_{\text{mean}}$ ). Within lesion heterogeneity will be explored using the method described by Kurland et al (16).

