### **5.8 Reproducibility Research Imaging Session (Optional)**

Up to 5 PR+ patients who agree to participate in this optional sub-study of the trial will undergo a second (test-rest) study. The test re-test exam cannot be performed the same day but should be completed prior to any therapy or surgical excision. This will not delay any scheduled routine standard of care therapy or procedures for the patient. This optional sub-study will be offered to all patients at the time of consent until we have accrued 5 PR+ patients onto the sub-study.

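### Section 12.2.1 assesses test-retest reproducibility only by summaries for each reading, which, taken per scan, do not show how far two scans of the same patient differ

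*Combined protocol and SAP*

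**What the plan says.** Section 12.2.1 says that the reproducibility of the two uptake measurements "will be evaluated in the 5 subjects who elect to undergo a second imaging session". The only method it gives for this is an evaluation "using summary statistics of tumor FFNP uptake for each reading for PET/MRI", with each reader analysed separately. It names no within-patient difference, within-subject SD or CV, repeatability coefficient, intraclass correlation or limits of agreement, and it does not say which uptake measure is meant.

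The other places that mention the sub-study give only its size and timing:

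- Number of Subjects: "a subset of up to 5 PR+ participants will have test-retest FFNP scans".
- Section 5.8: "Up to 5 PR+ patients who agree to participate in this optional sub-study".
- Table 2, note j: "the second scanning session will be done 24 hours apart or within a maximum 14-day time frame".

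A paired method does appear in the next item, 12.2.2, where SUV values "will be analyzed with Bland-Altman plots and 95% limits of agreement". That item concerns agreement within and between readers.

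Section 5.5.6 says that the two readers "will undergo two sessions of image interpretation of FFNP-PET/MRI scans separated in time", with at least 4 weeks between sessions.

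**The concern.** Repeatability is a within-patient quantity: if the same woman is scanned twice with nothing changed, how much does her SUV move? It can be estimated only from the paired values. A table with the mean and SD of scan 1 beside the mean and SD of scan 2 discards the pairing.

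This is the first secondary objective, and the Introduction gives it weight: "It is important to validate the accuracy and reproducibility of quantitative tumor FFNP uptake". Patients in the sub-study have a second FFNP scan to answer this question. If only per-scan summaries were reported, the reader would learn about a group shift but not about the measurement error that applies to one patient's scan. A stable group mean could then be taken as evidence that single scans are repeatable. Leaving the statistic unnamed also leaves its choice until after the data are seen.

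A smaller looseness is the word *reading*. With two scans and two sessions per reader, a patient with one lesion could have 2 × 2 = 4 values per reader for each uptake measure, and no rule says which two are compared.

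**Working it through.** The plan gives no precision target, acceptance limit or calculation for test-retest, so there is no figure to reproduce. Three checks follow.

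**1. Can per-scan summaries identify repeatability?** The documents give no SUVs, so these are assumed: test 2, 4, 6, 8, 10; retest 2.2, 3.9, 6.1, 7.8, 10.2. The scan means are 6.00 and 6.04 and the SDs 3.16 and 3.15, whichever retest value belongs to whom.

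Formulas, with d = retest − test and n = 5:

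- Within-subject SD = √[Σ(d − d̄)² / (2(n − 1))], with the mean shift estimated. Here d̄ = 0.04 under every pairing, so Σ(d − d̄)² = Σd² − 5 × 0.04² = Σd² − 0.008.
- Within-subject CV = √(exp(s²) − 1), where s is the same quantity computed on log values.

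| Pairing | Correlation | Σd² | Within-subject SD | CV |
|---|---|---|---|---|
| In order | 0.998 | 0.14 | √(0.132/8) = 0.13 | 3.5% |
| Retests of patients at 2 and 4 exchanged | 0.91 | 6.94 | √(6.932/8) = 0.93 | 33% |
| 4 and 6 exchanged | 0.89 | 8.94 | √(8.932/8) = 1.06 | 22% |
| 6 and 8 exchanged | 0.91 | 6.94 | √(6.932/8) = 0.93 | 14% |
| 8 and 10 exchanged | 0.88 | 9.74 | √(9.732/8) = 1.10 | 13% |

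One neighbour exchange raises the within-subject SD about 7 to 9 times, and no per-scan summary changes. If the mean shift is taken as zero, SD = √(Σd²/10), and the five rows give 0.12, 0.83, 0.95, 0.83 and 0.99, which is the same picture. Over all 120 pairings the SD runs from 0.13 to 4.46 (0.12 to 3.99 with zero shift). The top of that range needs a correlation of −0.998. It is a mathematical bound, not something to expect.

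**2. How different are the group shift and one patient's change?** The ranges below are 95% ranges of retest/test with 5 patients and no true change, at assumed within-patient CVs. For one patient the range is exp(±1.96 × √2 × s) − 1, with s = √ln(1 + CV²). At a CV of 20%, s = 0.198 and 1.96 × √2 × 0.198 = 0.549, which gives −42% to +73%. The ratio of group means comes from a lognormal simulation (400,000 runs) with assumed between-patient log SDs of 0.4 and 0.6; the wider result is shown.

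| Within-patient CV (assumed) | Ratio of group means | One patient |
|---|---|---|
| 10% | −13% to +15% | −24% to +32% |
| 20% | −24% to +32% | −42% to +73% |
| 30% | −34% to +51% | −56% to +126% |

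At a CV of 20%, the upper ends on the log scale are ln 1.32 = 0.28 and 0.55, so one patient's range is about twice as wide.

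**3. What would a paired statistic deliver?** The 95% interval for the within-patient log SD is the estimate times √(df/χ²₀.₉₇₅) to √(df/χ²₀.₀₂₅), with df = n − 1.

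- 5 pairs, df = 4: √(4/11.14) = 0.60 to √(4/0.484) = 2.87.
- 4 pairs, df = 3: 0.57 to 3.73.
- 3 pairs, df = 2: 0.52 to 6.28.

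An observed CV of 20% from 5 pairs (log SD 0.198) would give a log SD interval of 0.119 to 0.569, which is a CV of about 12% to 62%.

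**The case against.** The best defence is that 12.2.1 sets out to evaluate the reproducibility of two measurements in patients scanned twice, so its target is clearly agreement within the patient. Summary statistics is a broad term that can cover summaries of differences. A reader might infer that the plan will fail to report within-patient variation; the documents do not support this. What stands is narrower: the statistic is not named, and the phrase used points to summaries for each reading rather than of differences.

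A reader might also infer that the word *reading* makes the analysis unworkable. That too goes beyond the text. The same sentence speaks of two measurements and a second imaging session, which point to scans, and variation between reading sessions has its own objective and method in 12.2.2. The word is loose and worth fixing, but it is a side issue.

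It is also fair that the sub-study is optional, small and descriptive, that no hypothesis, limit or other objective depends on it, and that five pairs can simply be listed. The interval in check 3 shows how little an index computed on five pairs can settle. This limits the importance of the point. It does not favour per-scan summaries, because listing the pairs and giving an honest interval is the way to show that imprecision.

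Finally, every SUV and CV above is assumed. The example shows what per-scan summaries cannot show; it does not predict FFNP's repeatability.

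**Conclusion.** The point holds as a low-severity improvement. The method stated for test-retest, taken in its natural sense of summaries per scan, does not measure how far two scans of the same patient differ, and no other section supplies a paired test-retest statistic. The Bland-Altman limits in 12.2.2 cover reader agreement only.

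The finding that per-scan summaries do not identify within-patient spread needs no assumption about FFNP. The sizes do: the 7- to 9-fold rise in within-subject SD rests on the assumed SUVs, and the roughly twofold difference between one patient's range and the group's rests on an assumed 20% CV. The primary correlation test and the other objectives are unaffected.

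**What to change.** Replace the method clause in 12.2.1 with:

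> For each reader, using the first reading session for both scans and one prespecified index lesion per patient (the largest biopsy-proven lesion), each patient's test and retest SUVmax will be listed and plotted. The within-patient log ratio (retest/test) will be summarised by its mean, the within-subject CV and the repeatability coefficient, with a 95% CI on n − 1 degrees of freedom (mean shift estimated), where n is the number of completed pairs (up to 5). Other uptake measures are supportive, and results are descriptive.

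This names the paired statistic and the lead uptake measure, and fixes the reading session, the lesion and the degrees of freedom. Tying n to completed pairs also reconciles the fixed 5 in 12.2.1 with the maximum of 5 given elsewhere.

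The cost is one clause and a little analysis work, with no new scans, readers or patients. The downside is a visibly wide interval, so the result must be presented as descriptive. Using one session and one lesion also leaves some readings out of this analysis; the second session still serves 12.2.2.

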### **3. STUDY AIMS/STUDY OBJECTIVES**

The goal of this research is to test the accuracy of PET/MRI imaging with F-fluorofuranyl norprogesterone (FFNP) for measuring progesterone receptor (PR) expression in patients with invasive breast cancer. We hypothesize that FFNP SUVmax from PET/MRI will correlate well against the semi-quantitative PR immunohistochemistry score.

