## 5. RESEARCH DESIGN AND METHODS

### 5.1 Study Design

This prospective, one-arm, single-institutional research study will enroll patients with invasive breast cancer scheduled for diagnostic breast MRI for preoperative staging/extent of disease evaluation. Eligible patients will be consented for participation in the research study which will be performed on a separate day from the clinical breast MRI, if already performed, but prior to surgery. Ideally, the research breast PET/MRI study should be performed prior to any interventions (i.e. biopsies) prompted by the clinical breast MRI if performed prior to the research study, but this is not required. The results of the FFNP-PET/MRI will not be used to guide patient management. However, the clinical breast MRI component of the examination will be interpreted and reported with management recommendation as per routine clinical care. Surgical management, radiation therapy, and adjuvant therapy will follow standard of care. A research-based Oncotype DX score will be obtained from the surgical specimen for research purposes only. The proposed work-flow is described in the schema above.

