## 12. STATISTICAL CONSIDERATIONS

### 12.1 Primary Objective

12.1.1 To compare FFNP uptake of biopsy-proven primary PR+ breast malignancies measured using PET/MRI with the reference standard of PR immunohistochemistry (IHC).

The primary objective is to compare FFNP  $SUV_{max}$  from PET/MRI with the PR immunohistochemistry semi-quantitative score obtained by using the Allred score (0-8) (1). The correlation of the two measures will be evaluated with Pearson's correlation coefficient. The null hypothesis is  $H_0: p_0=0.20$  and the alternative hypothesis is  $H_1: p_1=0.70$ .

A sample size of 21 patients achieves 80% power to detect this difference, using a two-sided hypothesis test with a Type I error of 5%, accounting for 1 dropout. Sample size calculations were done in PASS 14 (NCSS, LLC, Kaysville, Utah. <http://www.ncss.com>).

Other measures of FFNP uptake including  $SUV_{peak}$  (small fixed-size ROI centered on most metabolically active part of tumor),  $SUV_{mean}$  (average value), tumor-to-normal tissue uptake ratio, and total lesion uptake (functional tumor volume  $\times$   $SUV_{mean}$ ) will also be correlated with the PR immunohistochemistry semi-quantitative score obtained by using the Allred score.

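### Section 12.2.3 leaves the construction of the AUC interval open with at most 5 PR-negative subjects; a Wald/DeLong interval would under-cover, and any specificity quoted at the cut-point would be optimistic and very imprecise

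*Combined protocol and SAP*

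**What the plan says.** Section 12.2.3 uses ROC analysis to separate PR-positive from PR-negative cancers, with the pathology report as truth and one analysis per reader. For the AUCs it says that "their respective two-sided 95% confidence intervals will be calculated using logistic regression". The threshold rule is: "The optimal cut-off point will be determined by considering the FFNP uptake value with the maximum sensitivity and specificity".

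The number of negatives comes from the Protocol Summary, Number of Subjects: "Up to 5 subjects with PR-negative breast cancer will be enrolled". That is a ceiling without a minimum, and the documents do not say whether these subjects are part of the planned 21 or additional to them.

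The cut-point is a named secondary objective (section 3.2). Section 3 opens with "The goal of this research is to test the accuracy of PET/MRI imaging with" FFNP. Nowhere do the documents give a precision statement for this objective, an internal or external validation step, or an interval for sensitivity or specificity at the cut-point. The later work announced in section 2 has another purpose: "Further studies will be performed to test whether FFNP-PET/MRI can be used to distinguish patients with endocrine-sensitive from endocrine-resistant" disease.

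**The concern.** There are two separate points, both arising from the small PR-negative group.

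- **AUC interval.** Logistic regression names a model, but it does not by itself define a confidence interval for an AUC. The interval most ROC software attaches is of Wald/DeLong type, which relies on a large-sample variance in each group. With 5 subjects in one group that variance is poorly estimated. If every PR-positive value exceeds every PR-negative value, it is zero, so the interval vanishes just when the result looks best.
- **Accuracy at the cut-point.** Choosing the threshold that looks best in a sample, then reading sensitivity and specificity from that sample, flatters both. The smaller group suffers more, so specificity is the one at risk.

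What is at stake is how a secondary result reads. A bare AUC of 1.00 with a zero-width interval, or a bare specificity of 5/5, would look far more certain than the data allow.

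**Working it through.** **1. The plan's own figure.** No sample size is given for this objective. The only one, in section 12.1.1, is for the primary correlation: "A sample size of 21 patients achieves 80% power to detect this difference". The same section makes that test two-sided at the 5% level and allows for one patient dropping out. With Fisher's z, n = ((1.960 + 0.842)/(atanh 0.70 - atanh 0.20))² + 3 = (2.802/0.6646)² + 3 = 20.8. Exact power with 20 evaluable is 80.2%, and 20 + 1 dropout = 21. So 21 reproduces as a two-sided calculation for the correlation and carries no information on the precision of the ROC analysis. (The Protocol Summary calls the same test one-sided. That is a separate matter to reconcile.)

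**2. Assumptions, not document figures.** Uptake is binormal, with one lesion per patient and a true AUC of 0.80, 0.90 or 0.95. The rule is read as maximum sensitivity + specificity, with the threshold midway between adjacent observed values. All 5 PR-negatives are enrolled. Both 21 and 16 PR-positives are shown, because the split is not stated. There were 4,000 simulated trials per main setting.

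**3. AUC interval.** With m positives and n negatives:
- DeLong: AUC ± 1.96 √(S₁²/m + S₀²/n), where S₁² and S₀² are the sample variances of each subject's share of correctly ordered pairs.
- Newcombe: the values θ that solve (θ - AUC)² = 1.96² V(θ), where V(θ) = θ(1-θ)/(mn) × {1 + ((m+n)/2 - 1)[(1-θ)/(2-θ) + θ/(1+θ)]}.

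| Equal variances, true AUC 0.80 / 0.90 / 0.95 | 21 vs 5 | 16 vs 5 |
|---|---|---|
| DeLong coverage, nominal 95% | 85 / 80 / 71% | 84 / 77 / 65% |
| DeLong interval of zero width | 1 / 6 / 20% | 2 / 9 / 24% |
| Newcombe coverage | 97 / 96 / 96% | 96 / 96 / 96% |

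Repeat runs agree to within about 2 points, so equal-variance DeLong coverage is about 64-85%. With the PR-negative SD between one third and twice the PR-positive SD (21 vs 5), DeLong covers 54-91% and Newcombe 91-99%.

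At an observed AUC of 1 with 21 vs 5, the Newcombe lower limit is θ = 0.763. Check: V = 0.763 × 0.237/105 × {1 + 12 × (0.192 + 0.433)} = 0.0146, and 1.96² × 0.0146 = 0.056 = (1 - 0.763)². For 16 vs 5 the limit is 0.749. The mean estimated AUC (21 vs 5) was 0.800 / 0.898 / 0.950, so choosing a cut-point does not bias the AUC.

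**4. Specificity at the chosen cut-point, equal variances.**

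| True AUC (21 vs 5) | Apparent | True | Overstatement |
|---|---|---|---|
| 0.80 | 0.857 | 0.670 | 0.187 |
| 0.90 | 0.917 | 0.765 | 0.152 |
| 0.95 | 0.961 | 0.824 | 0.136 (unrounded difference) |

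For 16 vs 5 the overstatement is 0.179 / 0.152 / 0.125. Sensitivity is overstated by only 3-5 points.

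**5. How far that depends on the assumptions (21 PR-positives).**
- Unequal variances, midpoint threshold: 10-17 points.
- Threshold at an observed PR-positive value: 16 / 13 / 10 points with equal variances, and as low as 7 at an SD ratio of 0.33.
- Threshold at the adjacent lower observed value: 21 / 19 / 18 points.
- Only 4 negatives: 16-21 points; only 3: 19-26 points (equal variances, midpoint).

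**6. Imprecision.** When all n negatives are classified correctly, the exact lower limit is 0.025^(1/n). This gives 0.478 for 5/5, 0.398 for 4/4 and 0.292 for 3/3. For 4/5 the exact interval is 0.284-0.995.

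**The case against.** The strongest reply is that the plan commits to an AUC with an interval and to a cut-point, but not to a sensitivity or specificity. The AUC estimate is not biased by the search for a threshold. The objective is secondary in a small single-institution study, and section 5.1 states "The results of the FFNP-PET/MRI will not be used to guide patient management". All of this stands, and it sets the grade.

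Several stronger readings are tempting but unsupported:
- *The AUC interval is unspecified.* Level, sidedness and model are fixed; only the construction is open.
- *The interval will under-cover.* The documents do not name Wald or DeLong, so the coverage figures are conditional on that choice.
- *Complete separation breaks the AUC.* The logistic slope then has no finite estimate, but the AUC is rank-based and remains 1. The problem is the zero-width interval.
- *A perfect 5/5 will appear in about half to four fifths of trials.* That holds only with equal variances. Over SD ratios of 0.33-2 the share runs from about 30% to 99%, and mean true specificity given 5/5 from 69% to 90%.

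Leave-one-out estimation also offers little. It removes the average bias, but its root mean squared error for true specificity is 0.18-0.23, against 0.18-0.24 for the apparent value.

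**Conclusion.** The point holds as a minor one. With at most 5 PR-negative subjects the way the AUC interval is built matters, and section 12.2.3 does not say. A Wald/DeLong interval would cover about 64-85% (equal variances) or 54-91% (unequal), against 96-97% and 91-99% for Newcombe. Any specificity quoted at the cut-point would be optimistic by roughly 13-19 points with equal variances and a midpoint threshold, or about 7-21 points under the other variance ratios and placements tried with 5 negatives. It would also be very imprecise. These sizes rest on assumed binormal uptake, one lesion per patient and true AUCs of 0.80-0.95. The direction was the same in every setting tried.

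A reader might infer that the plan will report a misleading specificity, or that the primary result is compromised. The documents support neither: no such figure is promised, and the primary correlation does not use the cut-point.

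**What to change.** In section 12.2.3:

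1. Name a Newcombe score-type 95% interval for the AUC. It stays informative under complete separation: 0.76-1.00 for 21 vs 5, and 0.75-1.00 for 16 vs 5.
2. Attach exact (Clopper-Pearson) intervals to any sensitivity or specificity quoted at the cut-point, and state that the point estimates are apparent, not validated. The exact interval shows imprecision but does not correct the optimism. It needs one lesion per patient or an adjustment for clustering. Section 5.5.6 measures uptake by lesion, section 12.2.2 treats several tumours in one patient as independent, and section 12.2.3 names no unit.

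Leave-one-out values may be shown beside the apparent ones but are optional. The per-reader analysis can stay as planned.

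The cost is a few lines of text and code, with no extra patients or scans. The downside is wider, less favourable intervals for a secondary objective. Neither step removes the underlying limit of 5 or fewer negatives.
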